8.2.6.2. Definition of Attribution

The attribution of an adverse event to the study will be determined by the Principal Investigator or designated physician co/sub-investigator. The Principal Investigator or designee will record the determination of attribution on the appropriate adverse event or serious adverse event form.

For the purpose of this study, the attribution of an AE to PNEUMOVAX®23 or PREVNAR 13® will be determined using the descriptors in the following table:

| Code | Descriptor | Definition (guidelines) | |
|--------------------|------------|---|--|
| UNRELATED CATEGORY | | | |
| 1 | Unrelated | The adverse event is clearly not related to study. The event is completely related to an etiology other than the study product or study intervention (the alternative etiology must be documented in the study subject's medical record) | |
| RELATED CATEGORIES | | | |
| 2 | Unlikely | The adverse event is doubtfully related to study and likely to be related to factors other than study product or study intervention. | |
| 3 | Possible | The adverse event may be related to study. There is an association between the event and the administration of study product and there is a plausible mechanism for the event to be related to the study product; there may be also an alternative etiology, such as characteristics of the subject's clinical status and/or underlying disease | |
| 4 | Probable | The adverse event is likely related to study. There is (1) an association between the event and the administration of study product or study intervention, (2) a plausible mechanism for the event to be related to the study product, and (3) the event could not be reasonably explained by known characteristics of the subject's clinical status and or an alternative etiology is not apparent | |
| 5 | Definite | The adverse event is clearly related to study. There is (1) an | |

Attribution of adverse events

| association between the event and the administration of the |
|---|
| study product or study intervention, (2) a plausible |
| mechanism for the event to be related to the related to the |
| study product, and (3) causes other than the study product |
| have been ruled out and/or the event re-appeared on re- |
| exposure to the study product |

8.2.7. SAE Reporting Criteria and Procedures

The Principal Investigator will be notified by the study staff as soon as a staff member becomes aware of the SAE. In the absence of the Principal Investigator, a physician sub-investigator will be notified.

8.2.7.1. Notifying the Independent Safety Monitor and the NIAID Medical Officer of SAEs and pregnancy

The Principal Investigator will notify the ISM and the NIAID Medical Officer by email simultaneously of any related SAE within 24 hours of becoming aware of the event.

The investigator will be informed immediately of any pregnancy and will report all pregnancies within 24 hours to the ISM and the NIAID Medical Officer utilizing the SAE report form. This report is for tracking purposes only. All pregnancies that are identified during the study will be followed to conclusion and the outcome of each will be reported. The investigator will discuss with the participant and/or the treating physician the known possible risks of the investigational product(s) on the fetus. Monitoring of the participant will continue until the conclusion of the pregnancy, and a follow-up SAE report form detailing the outcome of the pregnancy will be submitted to the NIAID Medical Officer and Project Manager. Subject will not be terminated from the study if pregnancy occurred after day 30.

The investigator will also report within 24 hours to the ISM and the NIAID Medical Officer any of the following events:

- Guillain-Barré Syndrome
- Radiculoneuropathy
- Anaphylactoid reactions
- -Anaphylaxis

- Serum Sickness

For non-related SAEs, the Principal Investigator will notify the ISM and the NIAID Medical Officer by email simultaneously of any related SAE within 7 days of becoming aware of the event.

The initial SAE CRF should be signed by the PI or co-PI and include as much information as possible. The SAE case report form will re-submitted and signed by the PI or co-PI to the ISM the NIAID Medical Officer with updated relevant medical information as needed until the event is considered closed by the ISM and the NIAID Medical Officer.

The study biostatistician, PI or study data manager will provide the ISM and the NIAID Medical Officer with cumulative periodic safety reports (tables and data listings of all AEs, including SAEs) during the conduct of the study. Resulting memorandums following evaluations of safety data will be sent to the IRB as needed in accordance with IRB rules and regulations.

8.2.7.2. Notifying the FDA

N/A

8.2.7.3. Notifying the Institutional Review Board

The Principal Investigator (or co-PI) will ensure the timely dissemination of SAE information, including SAEs requiring expedited ISM review and resulting memorandums following evaluations of safety data, to the IRB in accordance with IRB regulations and guidelines.

8.3. Protocol Deviations

Deviations occur when the Investigator, site study staff, or participants fail to adhere to protocol requirements or when there is non-adherence to (GCP) as delineated in ICH E6 (R1) guidelines. NIAID will not allow any waivers or planned deviations from the protocol.

Upon determination that a protocol deviation has occurred, the study staff will a) notify the Principal Investigator, b) notify the NIAID Project Manager(refer to investigator's signature

page for contact information) and c) will complete the Protocol Deviation form. NIAID may request discussion with the Principal Investigator and the ISM to determine the effect of the protocol deviation on the study participant and his/her further study participation, the effect of the protocol deviation on the overall study and corrective actions.

The Principal Investigator will complete and sign the Protocol Deviation form and submit it to the NIAID Medical Officer and Project Manager, to the ISM Monitor and to the site IRB, per IRB regulations.

Identification of protocol deviations will be done through the quality manager at the study site, or the NIAID project manager and/or Medical Officer. Reviewing and reporting of minor protocol deviations will be discussed at the Hope Clinic monthly meetings and among the Hope Clinic investigators. Major protocol deviations will be discussed with the PI, the ISM and NIAID study teams and will be promptly communicated to the regulatory agencies as needed.

All study deviations will be captured in monthly reports along with safety data and forwarded to the study sponsor and the ISM.

9. SAMPLE SIZE CALCULATIONS AND STATISTICAL PLAN

9.1. Sample Size and Power Calculations

The study is explorative. Not enough preliminary data exists to support accurate calculation of the sample size. However we conducted a sample size analysis based on hypothetical scenarios and knowledge of similar studies. Based on previous studies performed at the Hope Clinic and the Vaccine Research Trials Center, the rate of subjects that become ineligible during the study (i.e. do not meet exclusion/inclusion criteria anymore, lost to follow-ups, unable to have blood draws) is between 5 to 10%. Assuming 10% attrition rate, 88 subjects will be recruited and 1:1 randomized into the two treatment groups, resulting in an expected 80 subjects for data analysis. The sample size is on-par with similar studies. In the case that the sample size of subjects missing any of the 4 draws required for the primary endpoint [meaning draws at days 1, 3, 7(\pm 1), and 30 (\pm 7)] is higher than 10% of the 88 subjects to be recruited for the study, we will recruit extra patients to maintain the target sample size of 80 subjects.

The randomization process will be detailed in the MOP. At the center of this study is the identification of generic innate signatures and finding their correlations with the adaptive immune response. The generic innate signatures will be identified from both traditional immune parameters measured by FACS/Luminex assays and array-based gene expression will be measured by microarray experiments. The generic innate signatures will be identified for different treatment groups separately. The traditional immune parameters and array-based gene expression that change after immunization are considered generic innate signatures. The traditional immune parameters and array-based gene expression that change after immunization are considered generic innate signatures. The traditional immune parameters and array-based gene expression that are correlated with the adaptive immune responses (day 30 OPA titers, day 30 IgG levels, day 180 serotype specific avidity indexes, plasmablasts also) are considered correlation signatures of the innate immune responses.

Both for sample size consideration and data analysis, we will use different stringency levels for the traditional immune parameters and microarray data, because the traditional immune parameters are measured with less noise, and a traditional immune parameter is more likely than an average gene to be associated with the immune response.

Primary Endpoint 1.

The innate signatures will be detected in each treatment group separately. A two-sided paired paired t-test will be used to test each immune parameter, in order to find immune parameters that change significantly over the baseline. As multiple immune parameters are studied, we use the alpha level of 0.01 to offset multiple testing. With 30 samples in each treatment group in the elderly, we can reject the null hypothesis of equal means with 80% power if the true effect size (mean difference/sigma) is 0.66, using a two-sided paired t-test and the alpha level of 0.01.

For the gene expression, again the innate signatures will be detected in each treatment group separately. The actual data analysis will be performed using the method Significance Analysis of Microarrays (SAM) with paired design. For sample size consideration, we will consider the simpler case of a paired t-test. As the number of genes tested is in the order of tens of thousands, we use the alpha level of 0.0005 to offset the effect of multiple testing. This means an average of one false positive for every 2000 null genes tested, which is an acceptable level as we expect >100 truly differentially expressed genes. In actual data analysis false discovery rate (FDR) will be used. With 30 samples in each elderly treatment group, we can reject the null hypothesis of equal means with 80% power if the true effect size (mean difference/sigma) is 0.88, using a two-sided paired t-test and the alpha level of 0.0005.

Primary Endpoint 3, Secondary Endpoints 2&4.

The correlation signatures will be identified for each treatment group separately. The innate signature markers/genes identified in the analysis of Primary Endpoint 1 will be used in this step for the identification of correlation signature. For the traditional immune parameters, with 30 samples in each elderly treatment group, at the alpha level of 0.01, we can reject the null hypothesis of zero correlation with 80% power if the true correlation is 0.57 using a two-sided test for Pearson's correlation coefficient.

For the gene expression data, the actual data analysis will be performed using SAM with quantitative outcome. For sample size consideration, we will consider the simpler case of testing the significance of Pearson's correlation coefficient. We use the alpha level of 0.005 to offset the effect of multiple testing. This means an average of one false positive for every 200 null genes tested, which is an acceptable level as we expect the number of innate signature genes under study will be in the hundreds. The alpha level used here is different from that in

Primary Aim 1, because the numbers of multiple tests being conducted are different (several hundreds v.s. tens of thousands in Aim 1). With 30 samples in each elderly treatment group, at the alpha level of 0.005, we can reject the null hypothesis of zero correlation with adaptive immune responses with 80% power if the true correlation is 0.60 using a two-sided test for Pearson's correlation coefficient.

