7. STUDY VISITS AND PROCEDURES

7.1 Enrollment and Randomization

This research study will be explained in lay terms to each potential research participant. The potential participant will sign an informed consent form before undergoing any study procedures. Participants who are deemed eligible for the study (see sections 4.1 and 4.2) will be enrolled and assigned a unique participant number. Approximately eighteen months are needed for enrollment. The duration of participation for each subject is approximately 6 months. An additional optional blood draw will be offered 2-3.5 years after enrollment.

Eighty eight subjects (22 subjects (ages 25-40) and 66 subjects (ages 60-89)) will be randomized to receive PPV23 or PCV13 in a 1:1 ratio.

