9.2. Data Analysis

9.2.1. General considerations

The young treatment groups are of limited size. The main purpose of the young treatment groups is to provide some indication whether the elderly respond to the vaccines differently than the young. By themselves, the young groups do not have sufficient statistical power to generate reliable innate and correlation signatures. However when used in comparison against elderly groups, and by only considering biological pathways (collections of genes contributing to the same biological process) that are affected by the vaccine, they can provide some indication as to how different the response is in the elderly compared to the young. Thus for data analysis, the young treatment groups will be used only in exploratory endpoints. The primary and secondary endpoints will focus on the elderly groups.

The analyses will be based on population with critical time points met, defined as those who received vaccine per label and got the 4 draws required for the primary endpoint, i.e. draws at days 1, 3, 7 (\pm 1), and 30 (\pm 7) within the required windows. Data from the study will be analyzed using the statistical software R³¹. High-throughput data will be analyzed using appropriate methods, either by stand-alone software or modules in leading statistical softwares, e.g. the Bioconductor in the R framework³². For cytokine data, missing values will be dealt with using multiple imputations. For microarray data, nearest neighbor method and local least squares may be used to fill missing values. Unsupervised learning techniques such as PCA, PLSDA, clustering, and factor analysis ³³ will be used for the visualization and identification of global patterns. For descriptive endpoint (primary endpoint 2), we will generate summary statistics, and visualize the data using histograms and boxplots when applicable. For the identification of innate signatures, the two treatment groups will be analyzed separately.

Analyses of primary endpoints:

1. Identification of generic innate immune signatures [Traditional immune parameters measurements + array-based gene expression] at days 1, 3 and 7 post vaccination with either PPV23 or PCV13 in the elderly.

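### The top-up rule in section 9.1 protects 80 subjects in total, but the stated 80% power needs 30 evaluable subjects in each elderly vaccine arm, which the rule does not guarantee.

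*Combined protocol and SAP*

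**What the plan says.** - **Recruitment and loss (section 9.1).** "Assuming 10% attrition rate, 88 subjects will be recruited and 1:1 randomized into the two treatment groups", from which the plan expects 80 for analysis. It gives past loss as 5 to 10%.
- **Trigger (section 9.1).** Extra recruitment begins if the number missing any of the day 1, 3, 7 or 30 draws "is higher than 10% of the 88 subjects to be recruited for the study".
- **Target (section 9.1).** In that event "we will recruit extra patients to maintain the target sample size of 80 subjects". The age group and vaccine arm of the extra subjects are not specified.
- **Power (section 9.1).** The first statement reads "With 30 samples in each treatment group in the elderly, we can reject the null hypothesis of equal means with 80% power". The other three, one for gene expression and two for correlations, also use 30 per elderly treatment group.
- **Young groups (section 9.2.1).** "the young treatment groups will be used only in exploratory endpoints". There are 22 young subjects, 11 per vaccine (sections 1.6.1 and 7.1).
- **Replacement (sections 4.3, 6.4 and 8.1.4).** Subjects who terminate early or receive certain medications may be replaced so that power for the primary endpoint is kept. Section 4.3 extends this to subjects who miss a draw needed for that endpoint. Each clause refers to section 9.1 and none gives a number.

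**The concern.** The rule and the power statements count different things. Innate and correlation signatures are found in each elderly vaccine group separately, so power depends on the evaluable number in each of those two groups. The top-up rule watches one pooled count, to which the 22 young subjects contribute although they add nothing to the powered analyses. Up to eight losses leave 80 subjects and start no recruitment, wherever they fall.

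At stake is whether the stated 80% power describes the study that the rule would deliver. A lesser issue is that exploratory endpoint 4 compares the signature lists of the two vaccines. Arms of unequal evaluable size can give lists of different length through power alone.

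**Working it through.** **Inputs**
- Section 9.1: 88 recruited, 1:1 allocation, 5–10% loss, trigger above 10% of 88, target 80.
- Sections 3 and 7.1: 22 young and 66 elderly subjects.
- Section 9.1, all two-sided with 30 per elderly arm: paired t, d = 0.66, alpha 0.01; paired t, d = 0.88, alpha 0.0005; Pearson r = 0.57, alpha 0.01; Pearson r = 0.60, alpha 0.005.
- Assumptions: 33 elderly per arm (1:1 holding within the age stratum), and losses independent with the same rate q in every group.

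**Step 1. Reproduce the plan's power and see how it falls with n.** Paired t: noncentral t with n − 1 degrees of freedom and noncentrality d√n. Correlation: bivariate-normal power, with the noncentral t averaged over a random predictor.

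| Evaluable in arm | d = 0.66 | d = 0.88 | r = 0.57 | r = 0.60 |
|---|---|---|---|---|
| 30 | 79.7% | 79.8% | 79.5% | 79.4% |
| 29 | 77.8% | 77.2% | 77.6% | 77.4% |
| 28 | 75.8% | 74.3% | 75.7% | 75.2% |
| 27 | 73.7% | 71.2% | 73.6% | 72.9% |
| 25 | 69.0% | 64.3% | 68.9% | 67.9% |

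The plan's 80% is reproduced at n = 30 in all four scenarios.

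**Step 2. What the rule permits.** 0.10 × 88 = 8.8, so the trigger needs 9 losses. Eight losses leave 88 − 8 = 80, which meets the target. If the eight are elderly and evenly split, each arm has 33 − 4 = 29. If all eight are in one elderly arm, 33 − 8 = 25 remain.

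**Step 3. Expected numbers.** At 10% loss, 88 × 0.9 = 79.2 in total, but 33 × 0.9 = 29.7 per elderly arm, already just under 30. An expected 30 needs 30 / 0.9 = 33.3, so 34 per arm.

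**Step 4. How often an arm is below 30 with the trigger unfired.** Let i and j be the losses in the two elderly arms and k the losses among the young. Sum the product of the binomial probabilities b(i; 33, q) · b(j; 33, q) · b(k; 22, q) over all cases with i + j + k ≤ 8 and max(i, j) ≥ 4.

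| Loss rate q | Trigger unfired | Unfired and an elderly arm below 30 | Smaller arm in those cases: 29 / 28 / 27 or fewer |
|---|---|---|---|
| 5% | 96.8% | 12.8% | 77% / 19% / 4% |
| 7.5% | 78.6% | 22.2% | 72% / 23% / 5% |
| 10% | 47.7% | 18.7% | 69% / 25% / 6% |

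The middle column is lower at 10% than at 7.5% because the trigger fires in more than half of trials at 10%.

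**Step 5. The extreme case at 10% loss.** All eight losses in one elderly arm and none elsewhere: 2 × C(33, 8) × 0.1⁸ × 0.9⁸⁰ ≈ 0.00006.

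These probabilities cover only trials where the trigger has not fired. Once it fires, the result depends on who is recruited, which the plan does not state.

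**The case against.** The best defence is the replacement text. Sections 4.3, 6.4 and 8.1.4 have no 10% threshold and no pooled target. Their stated purpose is power for the primary endpoint, which is elderly-only. The team could use them before the ninth loss. This stands as mitigation, and it rules out saying that the plan leaves power unprotected. It does not close the gap: replacement is optional, no clause gives a number, and each points to section 9.1, where the only number to be maintained is the pooled 80.

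The second defence is that little is lost. Section 9.1 calls the study explorative and its scenarios hypothetical, and for gene expression the power calculations are a simplified stand-in for the planned method. A shift of a few points on assumed effect sizes is unlikely to change a decision. This stands, and it is why the point is minor.

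Third, the harm to the comparison of signature lists is limited. That comparison is exploratory and largely descriptive, and a floor of 30 would still allow 30 against 33. This also stands; the argument for change rests on the power statements.

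**Conclusion.** The rule is mis-specified: as written it can be met while an elderly arm is below the 30 on which every stated power figure rests. Under the assumptions of 33 per elderly arm and equal, independent losses, this happens without the trigger firing in about 13% to 22% of trials across the plan's own 5–10% loss range. The arm is then at 29 or 28 in about 94–96% of cases, with power of about 74–78%. Severity is minor.

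Three stronger readings are not supported.

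- **That power would drop to 64–69%.** This needs 25 in one arm, which the rule permits but which has a probability of about 0.00006 at 10% loss.
- **That the rule fails in two trials out of three.** At 10% loss some elderly arm is below 30 before any top-up in about 67% of trials. That count includes trials in which recruitment is then triggered, and it mostly reflects the expected 29.7 per arm.
- **That lost elderly subjects would be replaced by young ones.** The wording of section 9.1 does not exclude it, but nothing suggests that it is intended. It would run against the fixed 22/66 split and the purpose of the replacement clauses.

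**What to change.** In section 9.1, replace the pooled trigger and target with a count per elderly vaccine arm. If fewer than 30 subjects in either elderly arm have the required draws, randomise extra subjects within the 60–89 stratum until both arms reach 30. Leave the young group out of the count. Point the replacement clauses in sections 4.3, 6.4 and 8.1.4 to that number. If no top-up is done, restate the power at the evaluable number actually reached in each elderly arm.

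The cost is a sentence or two in section 9.1, cross-references in the three clauses, and possibly a few more elderly subjects. Without a top-up, the cost is a stated power about 2 to 6 points lower in the likely cases. No analysis method changes, and the plan already allows extra recruitment.

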4. Correlation of signatures of generic innate immune responses at days 1, 3 and 7 with serotype specific avidity indexes in a subset of up to 6 vaccinees per vaccine group at day 180 post vaccination with either PPV23 or PCV13 in the elderly.

The analysis will be conducted in each elderly treatment group separately. For traditional immune parameters, we will calculate the correlation coefficient between the immune parameter and the adaptive immune response (serotype specific avidity indexes at day 180 p) the p-values associated with the correlation coefficients will be used to select traditional immune parameters that are associated with the respective adaptive immune responses (serotype specific avidity indexes at day 180). The tentative selection criterion is p-value ≤ 0.01 .

For gene expression data, we will use the method Significance Analysis of Microarrays (SAM) with quantitative outcome to identify genes that are significantly associated with the respective adaptive immune responses (serotype specific avidity indexes at day 180). False discovery rate (FDR) will be used as selection criterion. The tentative selection criterion is $FDR \le 0.1$.

5. Comparison of the adaptive immune responses [Opsonophagocytosis assay (OPA) titers] at day 30 post vaccination with either PPV23 or PCV13 in the elderly.

Descriptive analysis, boxpots and histograms, will be conducted to present and visually contrast the data. Testing between the two elderly treatment groups will be conducted using unpaired t-test after proper data transformation. In the case that near-normality cannot be achieved with data transformation, we will resort to the Wilcoxon test.

Analyses of exploratory endpoints

1. Correlation of signatures of generic innate immune responses at days 1, 3 and 7 with adaptive immune responses [Opsonophagocytosis assay OPA titers specifically] at day 30 post vaccination among subjects in different age strata

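### Section 9.1 gives Secondary Endpoint 4 an 80% power statement based on 30 per elderly arm, but the endpoint is capped at 6 per arm, where the same test has about 6% power

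*Combined protocol and SAP*

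**What the plan says.** Section 9.1 places Secondary Endpoint 4 in a shared power paragraph, headed "Primary Endpoint 3, Secondary Endpoints 2&4". Two calculations follow, both for a two-sided test of Pearson's correlation:

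- Immune parameters (FACS and Luminex): "with 30 samples in each elderly treatment group, at the alpha level of 0.01, we can reject the null hypothesis of zero correlation". The power given is 80%, at a true correlation of 0.57.
- Gene expression: "With 30 samples in each elderly treatment group, at the alpha level of 0.005", 80% power at a true correlation of 0.60. The planned gene analysis is SAM; for sizing only, the plan says "we will consider the simpler case of testing the significance of" Pearson's coefficient.

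Secondary Endpoint 4 correlates the day 1, 3 and 7 innate signatures with day-180 avidity indexes. Section 9.2.1 (analyses of secondary endpoints, item 4) restricts it to avidity measured "in a subset of up to 6 vaccinees per vaccine group at day 180 post vaccination", and section 3.1.2.4 sets the same cap. On pooling, section 9.2.1 says "The analysis will be conducted in each elderly treatment group separately". For immune parameters "we will calculate the correlation coefficient between the immune parameter" and the avidity index, with selection tentatively at p ≤ 0.01. Genes are selected by SAM at FDR ≤ 0.1.

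The synopsis entry for Secondary Endpoint 4 mentions a subset without giving its size. Synopsis item 3, on the same assay and day, gives the cap. No other part of the plan states a power for this endpoint.

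**The concern.** The power statement uses n = 30, whereas the endpoint's definition allows at most 6 per test. The arms are not pooled, so nothing in the design brings n closer to 30. The only power the plan attaches to this endpoint is therefore one that its design cannot have.

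Two misreadings could follow. A reader who trusts the 80% could take the absence of selected markers as evidence that no correlation of about 0.57 exists, when the analysis had almost no chance of finding one. A reader could also accept the size of a selected correlation at face value, although with so few subjects only an extreme observed value can pass the threshold.

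**Working it through.** **Inputs.** Section 9.1: n = 30 per elderly arm; r = 0.57 with alpha 0.01 (immune parameters); r = 0.60 with alpha 0.005 (Pearson approximation for genes); two-sided test; 80% power. Sections 3.1.2.4 and 9.2.1: n ≤ 6 per arm, arms analysed separately.

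**Step 1: reproduce the plan at n = 30.** The Fisher z approximation is power ≈ Φ(atanh(r)·√(n−3) − z₁₋α/₂), plus a negligible opposite tail.

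- Immune parameters: atanh(0.57) = 0.6475; 0.6475 × √27 = 3.365; 3.365 − 2.576 = 0.789; Φ = 78.5%.
- Genes: atanh(0.60) = 0.6931; 0.6931 × √27 = 3.602; 3.602 − 2.807 = 0.795; Φ = 78.7%.

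The exact calculation (density of r under bivariate normality, t-test of r) gives 79.48% and 79.36%. The stated 80% reproduces.

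**Step 2: the same test at the cap, n = 6.** The multiplier √(n−3) falls from 5.196 to 1.732.

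- Immune parameters: 0.6475 × 1.732 = 1.122; 1.122 − 2.576 = −1.454; power about 7.3%.
- Genes: 0.6931 × 1.732 = 1.201; 1.201 − 2.807 = −1.606; power about 5.4%.

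Fisher z is rough at this size. The exact values are 6.25% and 4.02%, and simulation agrees.

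| n per arm | Power, r = 0.57, alpha 0.01 | Power, r = 0.60, alpha 0.005 | True r for 80% power (alpha 0.01 / 0.005) |
|---|---|---|---|
| 30 | 79.48% | 79.36% | close to the stated 0.57 / 0.60 |
| 6 | 6.25% | 4.02% | 0.954 / 0.968 |
| 5 | 4.04% | 2.41% | 0.978 / 0.986 |

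The n = 5 row is an illustration: the plan sets a ceiling, so the n = 6 row is the best case.

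**Step 3: what must be observed to pass.** The critical value is |r| = t/√(t² + n − 2). For n = 6 and alpha 0.01, t with 4 degrees of freedom is 4.604, so |r| = 4.604/√(21.20 + 4) = 0.917. For alpha 0.005, t = 5.598 and |r| = 0.942. For n = 30 and alpha 0.01, t = 2.763 and |r| = 0.463.

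**Step 4: inflation among selected immune parameters.** With a true r of 0.57, those passing p ≤ 0.01 by Pearson's test show a mean |r| of 0.947 at n = 6, against 0.613 at n = 30.

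**Step 5: if a rank coefficient were used.** Section 9.2.1 does not name the coefficient. With an exact Spearman test and no ties, a perfect ordering at n = 6 has p = 2/720 = 0.0028. The next attainable value, |ρ| = 0.943, has p = 12/720 = 0.0167. Only a perfect ordering passes 0.01. At n = 5 the smallest p is 2/120 = 0.0167, so nothing can pass.

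**Step 6: the plan's own benchmark.** Section 9.2.1 says the young groups are too small to yield reliable correlation signatures and keeps them to exploratory endpoints. They have 11 per vaccine (section 1.6.1). At n = 11, r = 0.57 and alpha 0.01, power is about 22%. The avidity subset has at most 6.

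**The case against.** The best case for the plan has four parts.

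- Section 9.1 says "The study is explorative" and calls its scenarios hypothetical, and the selection thresholds are labelled tentative. That excuses uncertainty about the true correlation. It does not excuse a sample size that the design itself rules out.
- The power sentences are explicitly conditional on 30 samples and are correct as such; only the heading links them to Secondary Endpoint 4. The cap is openly stated elsewhere. This is true, and it makes the repair small. The heading still names the endpoint, and the reader is given no other figure.
- This endpoint drives no design decision. Recruitment and top-up are tied to the draws needed for the primary endpoint. This stands, and it limits the consequence to how one secondary endpoint is described and read.
- The genes will be analysed by SAM, so the 4% figure describes only a sizing shortcut, and the plan never mentions a rank correlation. Both points stand. The power of SAM was not computed, the 0.917 bound applies only to immune parameters tested with Pearson's r, and the Spearman result is conditional on that choice of coefficient.

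**Conclusion.** The inconsistency is real and should be corrected. At the maximum of 6 per arm, power is 6.25% for immune parameters (r = 0.57, alpha 0.01) and 4.02% for the Pearson approximation for genes (r = 0.60, alpha 0.005), against the 80% stated. The stated figures remain valid for Primary Endpoint 3 and Secondary Endpoint 2, and no primary conclusion changes.

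The numbers assume bivariate normality, a two-sided Pearson test and a full subset of 6; fewer evaluable subjects would lower the power further. Confidence is high, because the error lies in which n was used and the gap is far larger than any difference between calculation methods (6.3% to 7.3% for immune parameters).

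**What to change.** In section 9.1, restrict the heading to Primary Endpoint 3 and Secondary Endpoint 2, and add a separate line such as:

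> Secondary Endpoint 4: at the maximum of 6 per arm, 80% power requires a true correlation of about 0.954 (alpha 0.01) or 0.968 (alpha 0.005, Pearson approximation). Power is about 6% at r = 0.57 (alpha 0.01) and about 4% at r = 0.60 (alpha 0.005, Pearson approximation), and lower with fewer than 6.

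Two optional additions would help: repeat the cap in the synopsis entry for Secondary Endpoint 4, and report the endpoint descriptively with confidence intervals.

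The cost is a text amendment, which section 12.1 requires to be approved before implementation, and a less favourable stated power for this endpoint. Subjects, assays, visits and the target of 80 analysed are unchanged. If descriptive reporting replaces signature selection and counts as a principal feature, section 9.4 also requires the change to be described in the final report and reviewed by the IRB, the independent safety monitor and NIAID.
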